**List of Adverse Events to be Reported:**

- \*Abdominal pain
- \*Creatinine
- \*Diarrhea
- \*Injection site Reaction
- \*Nausea
- \*Vomiting

All adverse events should be reported on the adverse event log and in ORIS regardless of whether they are on this list.

Asterisk (\*) denotes expected Adverse Events.

All SAEs are required to be reported to Rafael Pharmaceuticals via the provided SAE Reporting Form. All completed forms must be sent to [name] at Rafael. The Comprehensive Cancer Center of Wake Forest University will submit any applicable SAEs to the FDA.

SAE reports must be submitted to Rafael by fax to the following address:

Department of Regulatory and Clinical Affairs  
Rafael Pharmaceuticals, Inc.  
[name]  
[name]  
[contact]  
Telefax: [contact]

**7.2 STRC SAE Reporting Requirements**

The Safety and Toxicity Review Committee (STRC) is responsible for reviewing SAEs for CCCWFU Institutional studies as outlined in Appendix B. STRC currently requires that all unexpected grade 4 and all grade 5 SAE's on these trials be reported to them for review. This procedure is a part of the CCCWFU Data Safety Monitoring Plan that our institution has on file at the NCI. All CRM staff members assisting a PI in investigating, documenting and reporting an SAE qualifying for STRC reporting are responsible for informing a clinical member of the STRC committee as well as the entire committee via the email notification procedure of the occurrence of an SAE.

**7.3 WFUHS IRB AE Reporting Requirements**

Any unanticipated problems involving risks to subjects or others and adverse events shall be promptly reported to the IRB, according to institutional policy. Reporting to the IRB is required regardless of the funding source, study sponsor, or whether the event involves an investigational or marketed drug, biologic or device. Reportable events are not limited to physical injury, but include psychological, economic and social harm. Reportable events may arise as a result

of drugs, biological agents, devices, procedures or other interventions, or as a result of questionnaires, surveys, observations or other interactions with research subjects.

All members of the research team are responsible for the appropriate reporting to the IRB and other applicable parties of unanticipated problems involving risk to subjects or others. The Principal Investigator, however, is ultimately responsible for ensuring the prompt reporting of unanticipated problems involving risk to subjects or others to the IRB. The Principal Investigator is also responsible for ensuring that all reported unanticipated risks to subjects and others which they receive are reviewed to determine whether the report represents a change in the risks and/or benefits to study participants, and whether any changes in the informed consent, protocol or other study-related documents are required.

Any unanticipated problems involving risks to subjects or others occurring at a site where the study has been approved by the WFUHS IRB (internal events) must be reported to the WFUHS IRB within 7 calendar days of the investigator or other members of the study team becoming aware of the event.

Any unanticipated problems involving risks to subjects or others occurring at another site conducting the same study that has been approved by the WFUHS IRB (external events) must be reported to the WFUHS IRB within 7 calendar days of the investigator or other members of the study team becoming aware of the event.

Any event, incident, experience, or outcome that alters the risk versus potential benefit of the research and as a result warrants a substantive change in the research protocol or informed consent process/document in order to insure the safety, rights or welfare of research subjects.

## 8.0 Pharmaceutical Information

### 8.1 Pharmaceutical Accountability

Drug accountability logs will be maintained for all investigative agents used under this protocol. These logs shall record quantities of study drug received and quantities dispensed to patients, including lot number, date dispensed, patient identifier number, patient initials, protocol number, dose, quantity returned, balance remaining, and the initials of the person dispensing the medication.

### 8.2 Study Drug

#### Various Names of Investigational Drug

Chemical Name:

6,8-bis-benzylsulfanyloctanoic acid

Alternative Name:

6,8-bis(benzylthio)octanoic acid; or

6,8-bis-benzylsulfonyloctanoic acid

|                                      |  |
|--------------------------------------|--|
| Chemical Abstract Society (CAS) No.: | 95809-78-2   |
| Pharmacologic Class:                 | altered energy metabolism-directed (AEMD) compound |
| Code Name:                           | CPI-613  |
| Trade Name:                          | Bylantra (tentative)                               |
| Generic Name:                        | None   |

#### Description of CPI-613 Drug Product

CPI-613 is provided in 10-mL amber glass vials. Each 10-mL vial contains 10 mL of CPI-613 at a concentration of 50 mg/mL (in 1M triethanolamine [TEA, also called trolamine]), which is equivalent to 500 mg of CPI-613. The drug product of CPI-613 is a clear and colorless solution that is free of any particulate matter.

#### Handling of CPI-613

CPI-613 is an investigational drug and the toxicity in humans is not fully understood. All necessary precautions in handling potentially toxic chemicals must be strictly adhered to. Gloves and protective clothing must be worn when handling CPI-613. Avoid contact by all modes of exposure. If the solution contacts the skin, it must be washed immediately and thoroughly with soap and water. If the solution comes in contact with mucous membranes, the membranes must be flushed thoroughly with water. Spills should be picked up with absorbent material and the area must be washed at least 3 times with ethyl alcohol followed by water.

CPI-613 drug product is slightly photosensitive (Study# PHO-001). Therefore, after removal of CPI-613 drug product from the amber vials, CPI-613 drug product should be protected from excessive light before administration to patients.

#### Storage of CPI-613

CPI-613 should be stored under refrigeration, at 2°-8°C (36°-46°F), except when being prepared for administration.

If CPI-613 is to be transferred from one storage area to another, or is to be prepared for dosing, care must be taken to maintain appropriate product temperature.

UNDER NO CIRCUMSTANCES SHOULD CPI-613 BE FROZEN.

#### IV Infusion Sets, Syringes and IV Bags to be Used for Administration of CPI-613

CPI-613 must be administered IV by infusion, via a central IV catheter with D5W running at a rate of about 125-150 mL/hr. Subsequent sections describe the appropriate types of IV catheters, IV bags, syringes and clinical solutions that can be used in mixing and administering CPI-613 to patients.

Leaching of Diethylhexyl Phthalate (DEHP): CPI-613 can cause leaching of DEHP from IV infusion sets and IV bags (Study COM-003). Therefore, DEHP-containing IV infusion sets, IV bags or syringes should not be used in mixing or administration of CPI-613. Examples of syringes and extension set for syringe pump that do not contain DEHP (and therefore can be used in the administration of CPI-613) are:

Syringes: Kendall Monoject syringes, all mono-ject syringes are DEHP free.

Extension Set for Syringe Pump Use: All extension sets from MED-RX do not contain DEHP.

IV Infusion Sets: A compatibility study has been conducted showing that CPI-613 is compatible with 4 commonly used IV infusion sets (Study# COM-001). Therefore, these 4 types of IV infusion sets, and IV infusion sets that are made with the same materials, can be used to administer CPI-613. These IV infusion sets are:

PVC material - ADDitIV® Primary IV Set with Universal Spike, Backcheck Valve, 2 Injection Sites, DEHP-Free and Latex-Free, 15 drops/mL, REF V14453, B Braun Medical Inc.

Latex material - Interlink® System Secondary Medication Set, 10 drops/mL, 2C7451, Baxter Healthcare Corporation

PVC material - Surshield™ Safety Winged Infusion Set, 0.19 mL Volume, Latex-Free, DEHP-Free, SV\*S25BLS, Terumo Medical Products Hangzhou Co. Ltd.

Polyethylene material - Interlink® System Paclitaxel Set by Baxter HealthCare, Non DEHP: Polyethylene tubing with a 0.22 microfilter Item # 2C7558 10 drops/mL

Syringes: Compatibility studies (Studies# COM-001 and COM-002) have shown that CPI-613 drug product (50 mg/mL), and drug product diluted with D5W to various concentrations (1.6-25 mg/mL) are compatible with various types of syringes, as listed below. Therefore, any of these types of syringes, and syringes that are made with the same materials, can be used to administer CPI-613. Also, glass syringes can also be used, since glass (such as glass containers) is compatible with CPI-613 drug product.

Norm-Ject, polythelyene barrel, polyethylene plunger, latex free (Henke Sass Wolf GMBH) syringes  
Becton Dickinson syringes  
Terumo syringes  
Monoject syringes  
Glass syringes

Reconstitution and Administration of CPI-613

CPI-613 must be diluted from 50 mg/mL to 12.5 mg/mL with 5% Dextrose Water or D5W (i.e., 1 portion of CPI-613 diluted with 3 portions of D5W) prior to administration. The diluted drug product should be visually inspected for clarity. If haziness or precipitate is observed, do not use the diluted drug product for dosing. After dilution with sterile D5W, the solution is clear and has a pH of 8.4-8.8. The diluted CPI-613 drug product has been found to be stable for 24 hrs at room temperature and refrigeration temperature (Studies STA-010).

CPI-613 must be administered IV, via a central venous catheter that is free flowing, free of air in the dead space, and with D5W running at a rate of about 125-150 mL/hr. This is to minimize vascular irritation, inflammation and acute toxicity of CPI-613 (Study NCL-049). Accidental co-administration of extra air in the dead space of IV catheters during administration of CPI-613 has demonstrated the potential to induce acute toxicity of CPI-613 according to animal studies (Study NCL-049). Also, accidental leakage of CPI-613 into the perivascular space during IV administration, which prolongs exposure of perivascular tissue to CPI-613, can induce significant local inflammation according to animal studies (Studies NCL-027 and NCL-030).

CPI-613 must not be administered as a bolus, but by infusion via a central venous catheter, over a total of 2 hours. All doses of CPI-613 will be administered over 2 hours to simplify PK/PD analysis. The infusion will also minimize potential acute toxicity of CPI-613, according to animal studies (Study NCL-049). The following precautions must be taken when administering CPI-613:

- A. Confirmation of the placement of the IV line to ensure a lack of leakage of CPI-613 into the perivascular space.
- B. Confirmation that the IV line is free flowing, and with D5W running at a rate of about 125-150 mL/hr.
- C. Confirmation that the IV line is free of dead air space.
- D. Rotate the site of administration for different doses of CPI-613.
- E. Dilute CPI-613 drug product with D5W, as instructed in the study protocol.
- F. Administer CPI-613 by infusion, not as a bolus.

G. After administration of CPI-613, “slowly” flush the IV line with ~10 mL of D5W to remove residual CPI-613.

*Request for CPI-613*

CPI-613 must be requested from Rafael by the Principal Investigator (or authorized designees). CPI-613 may not be used outside the scope of this protocol, nor can it be transferred or licensed to any party not participating in this clinical study. Rafael policy requires that CPI-613 be shipped directly to the institution where the patient is to be treated. Rafael does not permit the transfer of CPI-613 between institutions (unless with prior written approval from Rafael). Requests must be submitted to Rafael by fax or email to the following address:

Department of Regulatory and Clinical Affairs  
Rafael Pharmaceuticals, Inc.  
[name]  
[name]  
[contact]  
Telefax: [contact]  
Email: [[contact]](mailto:[contact])

The following information must be provided in the request of CPI-613 from Rafael:

- Names of the principal investigator and the requestor (if different)
- Name of the study site
- Name of the pharmacist responsible for receiving and storing CPI-613
- Name of the person and address where CPI-613 is to be shipped to
- Amount (# vials) requested
- Date of request
- Date shipment expected
- Study Protocol (title and protocol#) for which the requested CPI-613 is to be used

*Procurement of Investigational Drug*

Relevant regulations require investigators to establish a record of the receipt, use and disposition of all investigational products. Investigators may delegate responsibility of drug ordering, storage, accountability and preparation to their designees.

The investigator, or the designee, will be responsible for dispensing and accounting of CPI-613 provided by Rafael and for exercising accepted medical and pharmacy practices.

Records of inventory, dispensation and disposition (vials received, source and dates) must be maintained. In addition, all doses dispensed should be accounted for by recording the date, study number and name, patient identification, patient initials, patient medical record number and balance forward. These records must be maintained and kept at the study site, and will be reviewed by Rafael, or its designee, during periodic monitoring visits.

#### Disposal of CPI-613

The following procedures are to be taken in disposal of CPI-613:

- During the study, store the used CPI-613 vials (which must be separate from the unused CPI-613 vials) at room temperature in an access-limited area. Alternatively, destroy the used CPI-613 vials according to institutional policy after documentation of the number of used CPI-613 vials and remaining volume in each used vial.
- At the end of the study, deface the label (both used and unused vials) with a permanent marking pen.
- For used CPI-613 vials (if not already destroyed according to institutional policy), after documentation of the number of used CPI-613 units and remaining volume in each container, the used containers should be destroyed at the site according to the institutional procedures for destroying toxic chemicals. A certificate documenting the destruction of used vials must be kept on file.
- All unused CPI-613 vials must be returned to Rafael at the address shown below. (Note: The return of the CPI-613 to Rafael, as well as the quantity returned, must be documented.)

Department of Regulatory and Clinical Affairs  
Rafael Pharmaceuticals, Inc.  
[name]  
[name]  
[contact]  
Telefax: [contact]  
Email: [contact]

## **9.0 Measurement of Effect**

### **9.1 Antitumor Effect**

Although response is not the primary endpoint of this trial, patients with measurable disease will be assessed by standard criteria for AML (*Blood*).

2010;115:453-474). Peripheral blood (PB) cell counts and samples of bone marrow aspirates will be assessed for changes in disease status. Hematologic improvement (HI) requires improvement in one of the three hematopoietic lineages compared with baseline measurements, and stable disease (SD) requires the absence of objective disease progression for at least 2 months. Relevant responses have to be confirmed by a repeat measurement at least 1 wk later. Assessments will be done as described above.

### 9.1.1 Definitions

Evaluable for toxicity. All patients will be evaluable for toxicity from the time of their first treatment with CPI-613.

Evaluable for objective response. Only those patients who have measurable disease present at baseline, have received at least one cycle of therapy, and have had their disease re-evaluated will be considered evaluable for response. These patients will have their response classified according to the definitions stated above. (Note: Patients who exhibit objective disease progression prior to the end of cycle 1 will also be considered evaluable.)

Overall Survival (OS): Time from enrollment on trial to death from any cause.

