## **5.6 Study Procedures – Assessment of Safety, Plasma Concentration, and Possible Anti-Tumor Efficacy**

*Safety Assessment:* The safety of CPI-613 will be assessed based on:

- physical exams
- vital signs
- clinical pathology

- clinical chemistry
- renal function
- hematology

For physical exams and vital signs, they are to be performed during screening (performed within 2 weeks prior to treatment with CPI-613) and after CPI-613 administration in Cycle 1. Beyond Cycle 1, physical exam and vital signs will be assessed within 5 days of the next cycle doses.

For clinical pathology (i.e., clinical chemistry, renal function, hematology and coagulation), they are to be performed during screening (performed within 2 weeks prior to treatment with CPI-613), and within 24 hrs prior to dosing. Creatinine results within the last 24 hours must be reviewed prior to CPI-613 dosing. For Day 1 of Treatment Cycle 1, pre-dose assessments of clinical pathology are not needed because the pre-enrollment results can be used. Beyond cycle 1, laboratory assessments will be assessed on at least day 1 and 5 of each cycle rather than prior to beginning each cycle.

For left ventricular ejection fraction assessments, they are evaluated during screening and prior to consolidation therapy. Additional assessments can be made at the discretion of the treating physician.

*Anti-Tumor Efficacy – A Secondary Endpoint:* Baseline anti-tumor efficacy (i.e., bone marrow biopsy) will be obtained within 2 weeks prior to the first dose of treatment cycle 1. Follow-up anti-tumor efficacy will be obtained on day 14 of cycle 1. In patients treated with additional treatment cycles beyond Cycle 1, anti-tumor efficacy will be assessed upon count recovery (defined as ANC>1000, freedom from RBC transfusions and platelets>100k) or day 42 from the first day of the cycle whichever comes first. Anti-tumor efficacy assessment will also be based on investigator and institutional routine monitoring of the disease progression of the patients, together with baseline evaluations performed prior to treatment with CPI-613. During maintenance therapy anti-tumor efficacy will be assessed after every 4th cycle.

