### **5.9 Criteria for Removal from Study**

Listed below are criteria for the discontinuation of the study. However, patients who fail to return for the follow-up visits will be contacted and queried as to the reason they have failed to complete the study with special attention to health status.

- A. Patients have the right to withdraw from the study at any time for any reason.
- B. The investigator has the right to withdraw patients from the study according to his/her discretion, if the investigator determines that continued participation is not in the patient's best interest. As an excessive rate of withdrawals can render the study not interpretable, unnecessary withdrawal of patients should be avoided. When a patient discontinues investigational treatment, the investigator should make every effort to contact the patient and to perform a final evaluation. The reason(s) for withdrawal must be recorded. Criteria for terminating subject's participation in the study are listed below:
  - Protocol defined disease progression significantly greater than expected
  - Unacceptable toxicity of the investigational product
  - Patient withdrawal of consent
  - Investigator's discretion
  - Undercurrent illness: a condition, injury, or disease unrelated to the intended disease for which the study is investigating, that renders continuing the treatment unsafe or regular follow-up impossible
  - General or specific changes in the patient's condition that renders the patient ineligible for further investigational treatment
  - Non-compliance with investigational treatment, protocol-required evaluations or follow-up visits
  - Termination of the clinical trial by the sponsor

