### Analysis Plan:

The primary objective of determining the feasibility of administering CPI-613 in combination with high dose cytarabine and mitoxantrone during induction, consolidation and maintenance therapies will be completed by determining the percentage of patients eligible for maintenance therapy who complete at least 3 cycles. If  $\geq 50\%$  of eligible patients complete 3 cycles of maintenance therapy we will consider this regimen feasible for future study. Given an estimated response rate of 50% and a 25% attrition to stem cell transplant, if we enroll 60 patients we should be able to assess feasibility of maintenance in approximately 22 patients. With 22 evaluable patients, a two-sided 95.0% confidence interval using the large sample normal approximation will extend 22% in either direction from the observed value when the expected value is 50%. Within a dose we should be able to estimate feasibility in 7 patients with a 95% confidence interval extending 36% in either direction.

Participants will also be followed and analyzed for secondary outcomes of response rate and overall survival both overall and by dose. Participants will be monitored for survival through routine follow-up visits. Confidence intervals will be calculated around the estimates of the response rate (CR and CRi). Assuming a response rate of 0.5, with 60 participants, we would be able to create 95 percent confidence intervals with a 0.13 margin of error (0.37, 0.63). We will use Kaplan-Meier estimation to analyze overall survival. The frequency of toxicities experienced by the participants will be presented by type and grade in an effort to monitor and report safety of the treatment.

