## APPENDIX C- Response Criteria:

Table 5. Response criteria in AML

| Category                           | Definition   |
|------------------------------------|--|
| Complete remission (CR)*           | Bone marrow blasts < 5%; absence of blasts with Auer rods; absence of extramedullary disease; absolute neutrophil count $> 1.0 \times 10^9/L$ (1000/ $\mu$ L); platelet count $> 100 \times 10^9/L$ (100 000/ $\mu$ L); independence of red cell transfusions                                    |
| CR with incomplete recovery (CRI)† | All CR criteria except for residual neutropenia ( $< 1.0 \times 10^9/L$ [1000/ $\mu$ L]) or thrombocytopenia ( $< 100 \times 10^9/L$ [100 000/ $\mu$ L])   |
| Morphologic leukemia-free state‡   | Bone marrow blasts < 5%; absence of blasts with Auer rods; absence of extramedullary disease; no hematologic recovery required   |
| Partial remission (PR)             | Relevant in the setting of phase 1 and 2 clinical trials only; all hematologic criteria of CR; decrease of bone marrow blast percentage to 5% to 25%; and decrease of pretreatment bone marrow blast percentage by at least 50%  |
| Cytogenetic CR (CRc)§              | Reversion to a normal karyotype at the time of morphologic CR (or CRI) in cases with an abnormal karyotype at the time of diagnosis; based on the evaluation of 20 metaphase cells from bone marrow  |
| Molecular CR (CRm)                 | No standard definition; depends on molecular target  |
| Treatment failure                  |  |
| Resistant disease (RD)             | Failure to achieve CR or CRI (general practice; phase 2/3 trials), or failure to achieve CR, CRI, or PR (phase 1 trials); only includes patients surviving $\geq 7$ days following completion of initial treatment, with evidence of persistent leukemia by blood and/or bone marrow examination |
| Death in aplasia                   | Deaths occurring $\geq 7$ days following completion of initial treatment while cytopenic; with an aplastic or hypoplastic bone marrow obtained within 7 days of death, without evidence of persistent leukemia   |
| Death from indeterminate cause     | Deaths occurring before completion of therapy, or $< 7$ days following its completion; or deaths occurring $\geq 7$ days following completion of initial therapy with no blasts in the blood, but no bone marrow examination available   |

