**APPENDIX F - CCCWFU 22215 Data Collection Form – FOLLOW-UP Form**  
**Response Evaluation Criteria for Acute Myeloid Leukemia**

PID: \_\_\_\_\_

Date: \_\_\_\_ / \_\_\_\_ / \_\_\_\_

Please check the response that applies to this patient:

- Complete Remission (CR)
- Complete Remission with Incomplete Recovery (CRi)
- Morphological Leukemia-Free State
- Partial Remission (PR)
- Cytogenetic Complete Response (CRc)
- Molecular Complete Response (CRm)

Treatment Failures

- Treatment Failure due to Resistant Disease (TFRD)
- Treatment Failure due to Complications of Aplasia (TFCA)
- Treatment Failure of Indeterminate Cause (TFIC)
- Induction Death
- Relapse

Hematologic Response Criteria

- Erythroid Response (pretreatment, <11g/dL)
- Platelet Response (pretreatment, < 100 x 10^9/L)
- Neutrophil Response (pretreatment, <1.0 x 10^9/L)
- Progression or Relapse after (HI) Hematologic Improvement

\*If the patient has experienced relapse please record cytogenetics and molecular abnormalities at the time of relapse on next page. (not required per protocol)

Treating Physician Signature: \_\_\_\_\_ Date: \_\_\_\_\_

PI Signature: \_\_\_\_\_ Date: \_\_\_\_\_

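### The denominator of the response rate is not settled: Section 9.1.1 drops patients lost before re-evaluation, while Section 10 and Appendices C and F point to counting them

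*Combined protocol and SAP*

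**What the plan says.** Three parts of the combined protocol and SAP bear on who is counted in the CR/CRi rate.

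- **Section 9.1.1 (Definitions)** restricts response evaluability to patients with measurable disease at baseline who "have received at least one cycle of therapy, and have had their disease re-evaluated will be considered evaluable for response". The one exception admits patients with objective progression before cycle 1 ends. Section 9.1 has the same slant: "patients with measurable disease will be assessed by standard criteria for AML".
- **Section 10 (Analysis Plan)** does not refer to that set. It says "Participants will also be followed and analyzed for secondary outcomes of response rate and overall survival both overall and by dose", and bases precision on the number enrolled: "Assuming a response rate of 0.5, with 60 participants, we would be able to create 95 percent confidence intervals".
- **Appendix C**, under treatment failure, has a category of death from indeterminate cause that covers "Deaths occurring before completion of therapy". The follow-up form in **Appendix F** has a box for "Induction Death" under treatment failures.

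Two further passages affect how many patients are involved. Section 5.6 says "Follow-up anti-tumor efficacy will be obtained on day 14 of cycle 1", so a patient lost after that marrow may already count as re-evaluated. For patients who stop treatment, Section 5.9 says "the investigator should make every effort to contact the patient and to perform a final evaluation", but Appendix C has no category for a patient on whom no such evaluation is obtained.

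**The concern.** An analyst could follow Section 9.1.1 or Section 10 and report different response rates from the same data. The patients at issue are those who die, withdraw or are lost before any reassessment and without documented progression. They cannot be recorded as CR or CRi, so removing them from the denominator can only raise the rate. Response is to be reported overall and by dose, so dose cohorts with different early loss would be inflated by different amounts.

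Section 10 also plans an exploratory comparison with a historical response rate of 41%. If the two cohorts use different denominators, that comparison is distorted, and the direction depends on which cohort uses which set. The trial is open-label, so a denominator left open could be chosen with the outcomes in view.

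**Working it through.** **Inputs.** From Section 10: 60 participants, assumed response rate 0.5, stated margin 0.13 (0.37, 0.63), historical rate 41%, one-sided level 0.05, alternative 56%, power 70%. The share d lost before re-evaluation is not in the documents; 5% and 10% are assumptions. The historical 60-day mortality of 29% is not used as d, because many such deaths could follow the day 14 marrow.

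**The plan's own figure.** Half-width = 1.96 × √(0.5 × 0.5/60) = 0.127, giving 0.37 to 0.63, as stated.

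**Effect on the reported rate.** If every lost patient is a non-responder, the evaluable-only rate is p/(1-d). For 30 responders among 60 treated:

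| Lost | Denominator | Rate | Half-width | 95% interval |
|---|---|---|---|---|
| 0 | 60 | 50% | .127 | 0.37 to 0.63 |
| 3 (5%) | 57 | 53% | .130 | 0.40 to 0.66 |
| 6 (10%) | 54 | 56% | .133 | 0.42 to 0.69 |

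The precision hardly changes; the estimate moves. In a dose cohort of 20 with 10 responders, 10/20 = 50% becomes 10/19 = 53% or 10/18 = 56% with one or two patients lost.

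**Opposite direction.** Section 9.1.1 also excludes patients without measurable disease or with an incomplete cycle, and some of these could respond. With a1 early losses and a2 excluded responders the rate is (30 - a2)/(60 - a1 - a2). For a1 = 3 and a2 = 0 it is 30/57 = 53%; for a1 = 3 and a2 = 3 it is 27/54 = 50%, and the two effects cancel.

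**Comparison with 41%.** The exact one-sided binomial test with n = 60 rejects at 32 or more responders. Its size is .036 and its power at 56% is .709, close to the planned 70%. The denominator behind the 41% is not given, so three cases were computed at d = 5% and 10%:

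- **A.** Historical over all treated, trial over evaluable: evaluable number ~ Bin(60, 1-d), responders with probability .41/(1-d) under the null.
- **B.** Historical over evaluable, trial over all 60: response probability .41(1-d) under the null and .56(1-d) under the alternative.
- **C.** Both over evaluable patients.

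| Case | Size, d = 5% | Size, d = 10% | Power, d = 5% | Power, d = 10% |
|---|---|---|---|---|
| A | .07 | .13 | – | – |
| B | .017 | .007 | .54 | .37 |
| C | .036 | .035 | .69 | .66 |

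Section 10 names a chi-square test for response. Uncorrected, it rejects at 31 or more, with size .062 and power .790 when nobody is lost. Case A then gives size .097 and .163. Case B gives size .031 and .014, with power .644 and .473. Case C gives size .052 and .048, with power .742 and .711. The pattern is the same under both tests.

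**The case against.** The strongest reply is that a response set is defined. Section 9.1.1 is specific, and the general word used in Section 10, in a sentence that also covers survival, can be read as subject to it. The 60 sits in a precision illustration, and a margin that rounds to 0.13 fits any n from 53 to 61, so it does not prove an all-enrolled denominator. Appendices C and F classify outcomes and do not set a denominator. The affected group may be small: the day 14 marrow counts as follow-up, early progressors are kept, and entry requires expected survival above 3 months. Response is secondary and the historical comparison exploratory. A shift of 3 to 6 points lies inside the 13-point margin, and early deaths still appear in overall survival and 60-day mortality.

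Much of this stands as a limit on the consequence. The evidence from the figure 60 is suggestive only, d is unknown, and no decision rule uses the response rate. It does not remove the problem. If Section 9.1.1 does govern, the plan's rule drops early deaths that its own response criteria call treatment failures, and the rate is inflated by rule. If Section 10 governs, the Section 9.1.1 definition has no stated use.

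A further fair point is that Section 10 plans 67 patients, including 7 already accrued at 2,500 mg/m², while its precision uses 60. That is a separate mismatch, but a new denominator definition has to address it.

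**Conclusion.** The concern holds, and it should be fixed. The documents do not reconcile the response denominator, and the one explicit definition leaves out patients who cannot be responders. At an assumed loss of 5% to 10%, with all lost patients non-responders and no responders excluded, a true 50% reads as 53% to 56%, overall or in a cohort of 20. Exclusion of responders under the other conditions in Section 9.1.1 could offset this.

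For the comparison with 41%, the harm comes from mismatched denominators. Depending on which cohort uses which set, exact size rises to .07 to .13 or power falls to .54 to .37. With matched evaluable sets, size is essentially unchanged and power falls only to .69 to .66. The primary feasibility endpoint is not affected.

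**What to change.** In Sections 9.1.1 and 10, define the denominator for the CR/CRi rate, its confidence intervals and the by-dose estimates as all patients who received any CPI-613. State whether the overall rate includes the 7 patients accrued at 2,500 mg/m², so that its N is explicit. Count early deaths as treatment failures in line with Appendix C and, as a stated convention, count patients with no post-baseline assessment as non-responders.

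Keep the present Section 9.1.1 set for a sensitivity analysis, reporting the number excluded for each reason, overall and by dose. For the exploratory comparison with 41%, apply the same denominator definition as the historical cohort and say what it is.

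The cost is one definition in Section 9.1.1 and a few sentences in Section 10, with no new data collection. The historical cohort's denominator has to be looked up, and the reported response rate may be slightly lower.
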